## APPENDIX B EQUIPMENT LIST

The following equipment will be supplied to an investigative site for the duration of the study provided that the site does not already have such equipment available for use. This equipment loan will be documented in the Clinical Trial Agreement, which indicates that the equipment is to be returned to Abbott Medical Optics at the completion of the study.

- One M&S Technologies CTS-1000 Smart System
- One Auto-Adjusting Monitor Calibration System
- Light meter
- DVD recorder (if necessary)
- Neutral density trial frame lenses for mesopic testing
- Tape measure (meters)
- NeurOptics Pupillometer
- AMO Laptop

## APPENDIX C      MANUAL OF TESTING PROCEDURES

**Anterior Segment Examination** shall be performed via biomicroscopic slit-lamp exam for determination of anterior segment medical findings including but not limited to the adnexa, conjunctiva, sclera, cornea, and iris. The corneal should be examined in detail and the following items graded on a scale of (0 to 4+, 0=clear): overall corneal clarity, any abnormalities such as corneal infiltrates, opacities in the lamellar bed, and density of the scar around the edge of the flap (for LASIK).

**BSCVA (Best Spectacle Corrected Visual Acuity)** shall be measured using the M & S Technologies CTS-1000 Smart System in logMAR format (100% contrast) at a test distance of 4 meters and calibrated to a photopic luminance of 85 cd/m^2 (80-110 cd/m^2). BSCVA testing is to be performed with the 4.0-meter manifest refraction in place; no refractive adjustment is necessary for BSCVA measurement. Detailed instructions for performing BSCVA testing are provided in **Appendix G**.

**Corneal Topography** shall be measured with the iDesign System or any other Scheimpflug or Placido disk-based system and the same device should be used at every visit. Images will be retained by the Investigator.

**Cycloplegic Refraction** shall be performed following installation of 1 drop of tropicamide 1% at least 30 minutes prior to determine the subject's refraction without accommodation.

**Dilated Fundus Examination** shall be performed following installation of mydriatic agents at least 30 minutes prior to determine the status of the ocular media, retina and lens.

**iDesign Advanced WaveScan Studio™ System** measures the refractive error and wavefront aberrations of the human eye using a Hartmann-Shack wavefront sensor. Preoperatively, a minimum of three measurements shall be taken or until an exam is selected for treatment; a minimum wavefront diameter of 4.0 mm for preoperative measurements is required. Postoperatively, at least one measurement is required at designated study exams. Every effort shall be made to obtain measurements with the largest wavefront diameter possible at each visit.

**Intraocular pressure** is to be measured using applanation tonometry and is to be performed after manifest refraction, vision tests, keratometry, topography, aberrometry, biomicroscopy, and before pachymetry.

**Keratometry** (not simulated K) shall be conducted preoperatively using the iDesign System AND an auto or manual keratometer. The same additional keratometry method is to be used at each required visit, e.g., if auto keratometry was recorded at the preoperative exam, all postoperative keratometry readings should be auto K's. Do not use "sim K" from the corneal topography unit.

**Lighting levels and lane calibration** will be assessed by a representative of the Sponsor to ensure the lane length and lighting conditions are consistent across sites. The site or Sponsor designee will verify the M & S Technologies CTS-1000 Smart System luminance level of 85 cd/m^2 (80-110 cd/m^2) with the auto-adjusting monitor calibration system at the start of each subject visit during the active enrollment and follow-up period. Verification of the screen luminance level will be recorded.

**Manifest Refraction** is to be performed using the phoropter and the M & S Technologies CTS-1000 Smart System in logMAR format (100% contrast) at a distance of 4.0 meters and calibrated to a photopic luminance of 85 cd/m^2 (80-110 cd/m^2). Manifest refractions to be performed using the Maximum Plus refraction method as detailed in **Appendix E**. Because 4.0 meters is not optical infinity, refraction adjustments are necessary for some vision tests to ensure proper vision testing taking into account test distance and refraction distance. **Appendix F** lists the refraction adjustments required for the various different vision tests using the 4.0-meter refraction.

**Mesopic Luminance** is defined as 3 cd/m^2 (2.5-3.5 cd/m^2).

**Mesopic Ambient Lighting** is defined as 30 – 50 lux.

**Mesopic Vision Testing** is to be performed using the 1.5 neutral density filters with the M & S Technologies CTS-1000 Smart System in ETDRS format (100% contrast).

**Mesopic Pupil Size Measurement** is to be performed under mesopic room lighting conditions of 30 – 50 lux. To set room lighting to 30 – 50 lux, turn off all the lights in the room, adjust the ambient light with the dimmer switch until the room lighting is dim to dark and verify with a light meter. Mesopic pupil size should be measured with the NeurOptics pupillometer.

**PRSVQ-Lasik Questionnaire** (2015 version) is a self-administered, validated assessment tool designed specifically for those who through correction of refractive error have normal visual acuity, but may still be experiencing problems in vision-related functioning and well-being. The PRSVQ questionnaire is to be administered preoperatively and at designated postoperative study exams.

**Pachymetry** to measure the corneal thickness shall be performed with an ultrasonic pachymeter preoperatively, intra-operatively (as applicable), and postoperatively.

**Photopic Luminance** is defined as 85 cd/m^2 (acceptable range of 80-110 cd/m^2).

**Photopic Pupil Size** is to be performed under photopic room lighting conditions of 480 – 520 lux. Photopic pupil size should be measured using the NeurOptics pupillometer.

**Refractive Stability (preoperative)** is defined as a change of  $\leq 1.00$  D in sphere or cylinder (based on a previous exam, medical records, or prescription) at least 12 months prior to the preoperative manifest refraction. Additionally, the astigmatic axis must also

be within 15 degrees for eyes with >0.50 D of preoperative and historical manifest cylinder.

**Refractive Stability Check for Contact Lens Wearers** is based on a change of not more than 0.50 D in MRS, MRC and as well as keratometric meridians on 2 separate occasions at least 7 days apart with readings following cessation of contact lens wear of 4 weeks for rigid contact lenses (toric or spherical) and 2 weeks for soft contact lenses (toric or spherical).

**Surgical Target** and planning is required prior to the operative exam. All eyes will be targeted for emmetropia. The iDesign 1.3-PRESBY TPS will be used to create a treatment shape for each eye that qualifies for the study. The TPS software used in this study is Version 1.3, which does not require any additional physician adjustments.

**UCVA (Uncorrected Visual Acuity)** shall be measured using the M & S Technologies CTS-1000 Smart System in logMAR format (100% contrast) at a test distance of 4 meters and calibrated to a photopic luminance (80-110 cd/m^2). UCVA testing is to be performed through a +0.25 D trial lens refractive adjustment to compensate for the 4 meter test distance. Detailed instructions for performing UCVA testing are provided in **Appendix G**.

## APPENDIX D MAXIMUM PLUS MANIFEST REFRACTION TECHNIQUE WITH CYLINDER REFINEMENT

Manifest refraction testing will be performed at 4 meters using the M&S Technologies CTS-1000 Smart System (M&S system) in logMAR format (100% contrast) and calibrated to a photopic luminance of 85 cd/m^2 (80-110 cd/m^2). The ambient room lighting shall be set to mesopic. **NOTE: Objective refraction by iDesign measurement must be used as a starting point for the Manifest Refraction.** Always ensure that the endpoint of refraction is maximum plus (or minimum minus) power that yields maximum visual acuity.

- 1) Occlude the fellow eye.
- 2) Place the iDesign system (4 mm Rx Calc) sphere (adjusted to 4 meters) and cylinder power and axis from the iDesign exam (vertex distance at 12.5mm) selected for treatment in the phoropter or trial frame preoperatively and from the single exam acquired postoperatively.
- 3) SPHERE: Starting with the objective refraction, refine the sphere to yield best visual acuity.
- 4) CYLINDER AXIS: Refine cylinder with a cross-cylinder and the objective cylinder refraction as the starting point. Refine axis first and power second, since the correct axis can be found with an incorrect power, but the correct power cannot be found with an incorrect axis.
  - a. Direct the subject's attention to 1 line above (larger letters) the best visual acuity. With the trial cylinder (axis and power) in the phoropter, introduce cross-cylinder for axis refinement. When asking the subject which cross-cylinder axis position is better, "one or two?", remind the subject to look at different letters on the line and report preference based on the overall clarity of the letters.
  - b. Refine the axis based on the subject's responses, using small steps (less than five degrees), until the subject reports no difference in the two choices.
- 5) CYLINDER POWER: Set the cross cylinder to refine cylinder power and present choices to the subject, reminding the subject to look at different letters on the line and report preference based on overall clarity of the letters. Reduce or increase trial cylinder power accordingly.
  - a. Maintain the spherical equivalent throughout cylinder power refinement by adjusting the sphere once for every two clicks of cylinder power change.
- 6) SPHERE CHECK: Introduce fogging lens (typically +0.75D sphere) and reduce in 0.25D steps until visual acuity shows no improvement.

## APPENDIX E CYCLOPLEGIC REFRACTION TECHNIQUE

The baseline refraction and the amount of accommodation that the subject habitually employs can only be determined by refracting with and without cycloplegia. The chief benefit of cycloplegia, therefore, is that it eliminates accommodation so that the examiner can make an accurate measurement of the refraction in the un-accommodative state. By comparing this result with a manifest refraction, the true refractive state of the eye and the accommodative tone can be established.

There are two pieces of information that are available from the cycloplegic examination that cannot be deduced from the manifest refraction alone:

- the magnitude of the refractive error free from the influence of accommodation; and
- the extent to which the accommodative tone influences the refractive state.

The following cycloplegic refraction technique is to be used throughout the study:

1. Instill tropicamide 1% and wait 30 minutes to allow for a full cycloplegic effect.
2. Start with the Manifest Refraction (maximum plus; refined from the objective iDesign measurement).
3. **Refine only the sphere magnitude so the least minus yields the most letters.**  
Do not refine or adjust the cylinder axis or the magnitude of the cylinder power.

## APPENDIX F REFRACTION ADJUSTMENTS

Postoperative study manifest refractions are to be performed using the M & S Technologies CTS-1000 Smart System (M&S system) in logMAR format (100% contrast) at a distance of 4.0 meters. Because 4.0 meters is not optical infinity, refraction adjustments are necessary to ensure proper vision testing taking into account test distance and refraction distance. The adjustment required (in diopters) is 1/test distance (in meters). To adjust a 4.0-meter refraction to optical infinity, -0.25 D is to be added to the sphere of the refraction to obtain a true distance (infinity) correction. When testing uncorrected visual acuity at 4.0-meters a +0.25 D sphere is required. In the case where the refraction distance (4.0 meters) and the vision test distance (4.0 meters) are the same, no adjustment is necessary. The following table lists the refraction adjustments required for the various vision tests in this study:

### Refraction Adjustments for Vision Testing

Vision Test	Test Distance	Correction/Adjustment
Uncorrected distance visual acuity (UCDVA)	4.0 m	+0.25 D adjustment only
Best corrected distance visual acuity (BCDVA)	4.0 m	No adjustment; manifest refraction only
Best corrected distance defocus curve testing	4.0 m	No adjustment; manifest refraction only
Uncorrected intermediate visual acuity (UCIVA)	67 cm	No adjustment
Distance corrected intermediate visual acuity (DCIVA)	67 cm	-0.25 D added to manifest refraction sphere
Uncorrected near visual acuity (UCNVA)	40 cm	No adjustment
Distance corrected near visual acuity (DCNVA)	40 cm	-0.25 D added to manifest refraction sphere

## APPENDIX G INSTRUCTIONS FOR USE OF M&S DISTANCE VISUAL ACUITY CHARTS

Distance visual acuity testing will be performed using the M&S Technologies CTS-1000 Smart System© computerized vision testing system (M&S system). This system provides a descending logMAR chart with 100% contrast proportionally spaced SLOAN letters. Each presentation is randomized and is consistent and repeatable. The system is calibrated for both distance to subject and pixels/inch so that optotypes precisely follow ANSI Z80.21-2010 and ISO 8596:2000 in regard to size, spacing between optotypes and spacing between lines.

**Figure 1: Example of logMAR 4.0 meter chart screen**

The M&S system background luminance is set to 85 cd/m^2 (range of 80 – 110 cd/m^2 is acceptable). Room lighting is to be set to a level lower than the illumination from the laptop screen. Ambient lighting should be mesopic (30-50 lux) to maximize pupil size. No surface (including reflective surfaces) within the subject's field of vision should be brighter than the chart background in luminance. The screen luminance will be verified at the start of each subject visit using the AMO-provided auto-adjusting monitor calibration system to ensure light levels are appropriate.

The M&S system laptop should be placed precisely at 4.0 meters (13 feet) from the subject for testing distance visual acuities. A laptop setting may be used to reverse charts for rooms that require "folding" via a mirror to reach a distance of 4.0 meters. Whether standard or "folded", measure and record the test distance accurately. If the room set-up does not allow the chart to be placed at precisely 4.0 meters, record the actual test distance used (e.g., 3.9 meters) and visual acuity measurements will be mathematically adjusted by AMO for the actual test distance used.

Subjects should be reminded prior to testing that squinting is not allowed. The technician is to observe the subject to ensure the subject is not squinting during visual acuity testing. If squinting is observed, the subject is to be reminded by the testing technician not to squint.

The right eye will be tested before the left eye; monocular testing should be completed for each measurement before binocular testing is done.

All subjects will be tested both uncorrected and best corrected, monocularly and binocularly. To test subjects monocularly, occlude the fellow eye in the phoropter or with an occluder (if trial lenses are used) and encourage subjects to read the smallest letters possible even if they have to guess. Visual acuity measurements are based on the total number of correctly read letters. Subjects should be instructed to start with the smallest line where they can read all of the letters. If they miss any letters, go up a line until they are able to read all the letters on a line, then continue to read each subsequently smaller line. The subject should be encouraged to read as many letters possible, even if they have to guess. Testing may be stopped when it is evident that no further readings can be made. Record the total number of letters read correctly on the chart. This will be displayed on the laptop screen along with the logMAR and Snellen acuity. Then begin testing for the fellow eye and repeat with both eyes together for binocular testing.

Perform monocular and binocular best corrected distance visual acuity testing in the same manner.

## APPENDIX H INSTRUCTIONS FOR USE OF M&S INTERMEDIATE VISUAL ACUITY CHART

Intermediate visual acuity will be measured using the M&S system intermediate charts designed for 67 cm.

The M&S system background luminance is set to 85 cd/m^2 (range of 80 – 110 cd/m^2 is acceptable). Room lighting is to be set at a level lower than the illumination from the laptop screen. Ambient lighting should be mesopic (30-50 lux) to maximize pupil size. No surface (including reflective surfaces) within the subject's field of vision should exceed the chart background in luminance.

The M&S system should be placed precisely at 67 cm from the subject for testing intermediate visual acuities.

Subjects should be reminded prior to testing that squinting is not allowed. Trial frames should be used for visual acuity testing with careful observation by the testing technician to ensure the subject is not squinting. If squinting is observed, the subject is to be reminded by the testing technician not to squint.

The right eye will be tested before the left eye; monocular testing will be completed for each measurement before binocular testing is done.

All subjects should be tested monocularly and binocularly, uncorrected and with distance correction in place. Visual acuity measurements are based on the total number of correctly read letters. Subjects should be persuaded to read the smallest letters possible even if they have to guess.

All subjects will be tested both uncorrected and best corrected, monocularly and binocularly. To test subjects monocularly, occlude the fellow eye in the phoropter or with an occluder (if trial lenses are used) and encourage subjects to read the smallest letters possible even if they have to guess. Visual acuity measurements are based on the total number of correctly read letters. Subjects should be instructed to start with the smallest line where they can read all of the letters. If they miss any letters, go up a line until they are able to read all the letters on a line, then continue to read each subsequently smaller line. The subject should be encouraged to read as many letters possible, even if they have to guess. Testing may be stopped when it is evident that no further readings can be made. Record the total number of letters read correctly on the chart. This will be displayed on the laptop screen along with the logMAR and Snellen acuity. Then begin testing for the fellow eye and repeat with both eyes together for binocular testing.

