## OVERALL STUDY DESIGN:

Structure:	Prospective, multi-center, non-randomized, contralateral, open-label, clinical study.
Number of sites:	Up to 4 sites in Canada
Duration:	9 months
Definitions:	PresbyT-LASIK is defined as the iDesign 1.3-PRESBY Treatment Planning Software, test treatment.  iDesign CustomVue is the iDesign Advanced WaveScan Studio™ System (software version 1.3), control treatment.
Administration:	Surgeons will perform wavefront-guided LASIK for the treatment of myopic refractive errors based upon

measurements obtained with the iDesign System using the STAR S4 IR™ laser and PresbyT-LASIK.

**Visit Schedule:** There will be 10 scheduled study visits: preoperative, contact lens dispense, contact lens follow-up, operative, 1-day, 1-week, and 1, 3, 6 and 9 months.

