#### **STUDY VISITS AND PROCEDURES:**

Inclusion and exclusion qualifications will be assessed at the preoperative visit according to the inclusion/exclusion criteria. The Informed Consent Document and Personal Health Information Protection Act Authorization must be signed by patients who agree to participate in the study prior to undergoing any study-specific procedures. After

determination that all inclusion/exclusion criteria have been met and the informed consent has been signed, subjects will be enrolled in the study. Subjects and study personnel performing the vision testing and refractions will be un-masked for the duration of the study.

The STAR S4 IR™ Excimer Laser System and the iDesign Advanced WaveScan Studio™ System will be used to perform wavefront-guided LASIK treatments. Both eyes of subjects will be treated in the study. Surgery will be performed with iDesign CustomVue treatments on the dominant eye and PresbyT-LASIK treatments on the non-dominant eye. The Dolman test will be utilized for eye dominance determination as described in **Appendix R**.

Key preoperative and postoperative data include iDesign measurements, visual acuities, manifest refraction, keratometry (iDesign and auto/manual), pachymetry, biomicroscopic slit-lamp findings, intraocular pressure, adverse events, ocular visual symptoms and patient reported outcomes (PRO) assessments of visual functioning and visual symptoms (using the PRVSQ for PRK/LASIK instrument). Ocular health and history are also assessed preoperatively. A chart summary of procedures required at each study visit is provided in **Appendix A**.

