## **4. STUDY DESIGN**

This study is a 9 month, prospective, multicenter, non-randomized, contralateral, open-label clinical study.

The study will be conducted at up to 4 sites in Canada and will include up to 34 test group treated eyes (of up to 34 subjects). Subjects must have both eyes treated in the study. The dominant eye will be treated with the control product; the non-dominant eye will be treated with test product. Analyses will be conducted at 6 months.

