## APPENDIX R OCULAR DOMINANCE - DOLMAN TEST

Hole-in-the-card test

1. Instruct the subject to hold a card with a hole in the middle with both hands at arm's length centered in front of themselves.
2. With both eyes open, view the examiner's nose standing on the other side of the room through the center hole.
3. The examiner is to look directly at the subject, and confirm which eye the subject is using for viewing i.e. the dominant eye.

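### Right-eye-first testing is partly confounded with treatment on the primary endpoint, because treatment follows ocular dominance and the paired t-test has no order term

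*Protocol*

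**What the plan says.** **Testing order.** Protocol Appendix H, which governs intermediate acuity at 67 cm, states: "The right eye will be tested before the left eye; monocular testing will be completed for each measurement before binocular testing is done". Appendix G gives the same rule for distance acuity: "The right eye will be tested before the left eye; monocular testing should be completed for each measurement before binocular testing is done". Appendix J starts the defocus curve with the right eye. Appendix I (near acuity) puts monocular before binocular testing but does not say which eye goes first.

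**Allocation of treatment to eye.** Protocol Section 4: "The dominant eye will be treated with the control product; the non-dominant eye will be treated with test product". The Synopsis and Appendix N agree. Dominance is found with the hole-in-card test in Appendix R, where the examiner is to "confirm which eye the subject is using for viewing i.e. the dominant eye". It can be either eye. The documents do not say what share of subjects is expected to be right-dominant.

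**Masking.** The Synopsis states: "Subjects and study personnel performing the vision testing and refractions will be un-masked for the duration of the study".

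**Analysis.** Protocol Section 20.2 and SAP Section 3.3 compare the eyes with a one-sided paired t-test at 0.025 on control minus test logMAR. Protocol Section 20.2 and SAP Section 3.4 do the same for near acuity. Neither document counterbalances order or includes a term for order, side or side of dominance.

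**The concern.** Pairing within a subject cancels whatever the two eyes share. Testing order is not shared: one eye is always read first and the other second. Acuity here is a letter count from an effort-dependent task in which subjects are urged to guess and the tester decides when to stop. The second eye may gain from practice or lose from fatigue. The 6-month visit is long: Appendix A lists corrected and uncorrected acuity at three distances, monocular and binocular, plus low-contrast, mesopic and defocus tests. The defocus curve alone has 11 levels, from +2.00 D to −3.00 D in 0.50 D steps.

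Order is set by right or left and treatment by dominant or non-dominant. If one side is dominant more often than the other, part of an order effect enters the treatment difference. Recruiting more subjects does not shrink that part, and the paired t-test cannot distinguish it from a treatment effect. The stated success criterion is p ≤ 0.025, so even a small shift changes the error rate of that decision.

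**Working it through.** **Inputs from the documents.** n = 34 pairs, SD 1.4 lines, design difference 0.7 line (Protocol Section 20.6, SAP Section 4); one-sided alpha 0.025 (Protocol Section 20.2, SAP Section 3.3); clinical threshold one line. One line is 0.1 logMAR (Protocol Section 6, safety endpoints) and one letter is 1/50 = 0.02 logMAR (SAP Appendix II), so one line is five letters. The SD is taken as that of the paired differences.

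**The plan's own figure.** The noncentrality is 0.7/1.4 × √34 = 2.915 on 33 degrees of freedom. The noncentral t gives power of 80.8%, both for two-sided 0.05 and for one-sided 0.025. The stated power of over 80% is confirmed. The standard error is 1.4/√34 = 0.240 line, and the smallest significant mean difference is 0.49 line.

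**Form of the bias.** Let e be the advantage, in lines, of the eye read second (negative for fatigue), and p the share of right-dominant subjects.

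- Right-dominant: the control eye is right and read first, the test eye second. The difference in favour of test shifts by +e.
- Left-dominant: the test eye is right and read first. The difference shifts by −e.
- Mean shift: p·e − (1 − p)·e = (2p − 1)·e.

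**Illustration.** Both p and e are assumptions. Error and power come from the noncentral t above with the mean shifted by the bias and the SD held at 1.4.

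| Size of bias (lines) | Example giving it | One-sided error if bias favours test | Power at 0.7 line if bias favours control |
|---|---|---|---|
| 0 | p = 0.5, any e | 2.5% | 80.8% |
| 0.04 | p = 0.6, size of e 0.2 | 3.6% | 76.1% |
| 0.08 | p = 0.7, size of e 0.2 | 5.1% | 70.8% |
| 0.10 | p = 0.6, size of e 0.5 | 6.0% | 67.9% |
| 0.20 | p = 0.7, size of e 0.5 | 12.5% | 52.5% |

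An order effect of 0.2 line is one letter. Adding the extra spread that the order term causes changes the error by at most 0.2 percentage points for e up to 0.3 line.

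**Check of the regression remedy.** Write each paired difference as τ + e·x, with x = +1 if the test eye was read second and −1 if first. With this coding the intercept estimates τ. If x is mean-centred, the intercept is the raw mean difference and the bias stays. Example: 24 of 34 right-dominant under the present order, e = 0.4 line, true effect 0. The mean of x is (24 − 10)/34 = 0.412, so the mean-centred intercept is about 0.4 × 0.412 = 0.16 line, against about 0 with +1/−1 coding.

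The variance of the adjusted estimate is multiplied by 1/(1 − x̄²), where x̄ is the mean of x. Power at 0.7 line is 80.7% when 17 of 34 test eyes are read second, 79.5% at 20, 77.1% at 22, 73.1% at 24 and 62.8% at 27. Regression alone, with the order left fixed, becomes costly as dominance becomes one-sided. With order balanced it costs almost nothing.

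**The case against.** A reader might infer that any practice or fatigue effect is wholly confounded with treatment. The documents do not support that. Side and dominance are different factors, and only the fraction |2p − 1| of an order effect reaches the comparison. It is nil at p = 0.5 and complete only if every subject has the same dominant side.

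A reader might also infer that the bias favours the test eye. Its direction is open: with p above 0.5, practice favours test and fatigue favours control, and with p below 0.5 both reverse. Nor can the point be carried over to the near endpoint as it stands, because Appendix I contains no right-first rule. There the order is unspecified, not fixed.

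The size can fairly be challenged too. By 6 months subjects have already done monocular DCIVA preoperatively and at 3 months. Chart presentations are randomised (stated for the distance chart), which limits letter memorising though not task learning or fatigue. Starting at the smallest fully readable line shortens the task. Nothing in the documents shows a one- or two-letter order effect at that stage. With an order effect of 0.2 line or less and p of 0.6 to 0.7, the bias is at most 0.08 line, small against the one-line clinical threshold. Preoperative monocular DCIVA could also cancel an order effect that is stable over time, but the plan does not use it that way.

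Finally, this is an open-label feasibility study in which dominance itself is fully confounded with treatment and testing is unmasked. Those are larger and separate matters. They limit how much weight this point deserves but do not answer it: the order bias can be avoided at little cost, and the error rate of the formal test is sensitive to shifts well below one line.

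**Conclusion.** The point holds in limited form. Right-first testing of DCIVA, with treatment fixed by dominance and a paired t-test without an order term, puts (2p − 1) times any order effect into the primary comparison. The result rests on the order effect being additive and on p differing from 0.5. The documents give neither quantity, so no particular bias can be asserted. Across the illustrated range, a bias of 0.04 to 0.20 line gives a one-sided error of 3.6% to 12.5% if it favours the test eye, or power of 76.1% down to 52.5% if it favours control. The upper end needs a large order effect together with clear imbalance in dominance. This does not invalidate the study, but it is worth removing because the remedy is cheap.

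**What to change.** **Testing manual.** In Protocol Appendices G, H and J, start with the right eye for odd subject numbers and the left eye for even ones, keep this for all visits, and record the order used. State the same order in Appendix I, which now gives none. Provided numbers are assigned without regard to dominance, this removes the bias in expectation.

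**SAP Sections 3.3 and 3.4.** Add a supportive regression of the paired difference on whether the test eye was read first or second, coded +1/−1 and not mean-centred. The intercept is then free of an additive order effect, including any chance imbalance left by the alternation. The covariate must be the recorded order: once the starting eye alternates, the side of the test eye no longer represents order. The planned paired t-test stays primary.

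**Cost.** One sentence in each appendix, one recorded field and one supportive model, with no extra visits or procedures. Technicians must follow and record the assigned order. The supportive model loses a little precision, almost none when order is balanced (80.7% against 80.8% power at an even split).
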